1 PROTOCOL SUMMARY

1.1 SYNOPSIS

Title:	Utilizing CT Based Imaging Parameters of Body Composition to Understand Heterogeneity of Response to Biologic Therapies in Severe Asthma Cohorts							
Study Description:	We plan to utilize University of Michigan EMR data to form a retrospective cohort of severe asthma patients on biologic therapies for asthma with CT imaging and known outcomes on therapy. We will then analyze these images using morphomics, a combination of high-throughput image analysis and deep learning techniques, to derive imaging biomarkers that will be able to predict therapeutic response to biologics. These biomarkers will then be tested in a second cohort from the University of Calgary to assess for validity.							
Objectives:	

Primary Objective:	To identify imaging biomarkers that are associated with the probability of any reduction in pre-treatment baseline exacerbation frequency in a severe asthma population on biologics	

Secondary Objectives:	
1. To identify imaging biomarkers that are associated with the probability of any post-treatment improvement of FEV1 of 5% or more2. To identify imaging biomarkers that are associated with the probability of any post-treatment reduction in maintenance OCS use	

Exploratory Objectives:	
1. To identify imaging biomarkers that are associated with the probability of any reduction in pre-treatment baseline hospitalizations for asthma2. To identify imaging biomarkers that are associated with the probability of any post-treatment improvement in ACT score3. To identify imaging biomarkers that are associated with the probability of any subjective post-treatment reduction in symptoms described clinically	

		Primary Objective:	To identify imaging biomarkers that are associated with the probability of any reduction in pre-treatment baseline exacerbation frequency in a severe asthma population on biologics	Secondary Objectives:	
1. To identify imaging biomarkers that are associated with the probability of any post-treatment improvement of FEV1 of 5% or more2. To identify imaging biomarkers that are associated with the probability of any post-treatment reduction in maintenance OCS use	Exploratory Objectives:	
1. To identify imaging biomarkers that are associated with the probability of any reduction in pre-treatment baseline hospitalizations for asthma2. To identify imaging biomarkers that are associated with the probability of any post-treatment improvement in ACT score3. To identify imaging biomarkers that are associated with the probability of any subjective post-treatment reduction in symptoms described clinically
Primary Objective:	To identify imaging biomarkers that are associated with the probability of any reduction in pre-treatment baseline exacerbation frequency in a severe asthma population on biologics							
Secondary Objectives:	
1. To identify imaging biomarkers that are associated with the probability of any post-treatment improvement of FEV1 of 5% or more2. To identify imaging biomarkers that are associated with the probability of any post-treatment reduction in maintenance OCS use							
Exploratory Objectives:	
1. To identify imaging biomarkers that are associated with the probability of any reduction in pre-treatment baseline hospitalizations for asthma2. To identify imaging biomarkers that are associated with the probability of any post-treatment improvement in ACT score3. To identify imaging biomarkers that are associated with the probability of any subjective post-treatment reduction in symptoms described clinically							
Endpoints:	Primary Endpoint:	Determine the cutoff value in chest wall muscle size/quality that optimally classifies patients that had and did not have any reduction in pre-treatment baseline exacerbation frequency (binary). Alternative (continuous): determine the strength of the linear/non-linear relationship						

	between continuous chest wall muscle size/quality and continuous change in exacerbation frequency
Secondary Endpoints:	
 1. Determine individual and combinations of body composition measures (phenotypes) associated with a 5% or greater improvement in FEV1 when compared to baseline FEV1 2. Determine individual and combinations of body composition measures associated with any reduction in maintenance OCS use when compared to baseline OCS use
Exploratory Endpoints:	
These endpoints may be limited in scope of analysis by the sample size within each of the outcome groups.
 
 1. Determine individual and combinations of body composition measures associated with any reduction in hospitalizations when compared to baseline hospitalizations 2. Determine individual and combinations of body composition measures associated with any improvement in ACT score when compared to baseline ACT score 3. Determine individual and combinations of body composition measures associated with any subjective improvement of symptoms when compared to baseline symptoms

Study Population:	Approximately 300 male or female subjects ages 18-85 with a diagnosis of asthma and on biologic therapy will be studied at the University of Michigan in Ann Arbor, MI, USA and approximately 200 male or female subjects over the age of 18 will be studied in the University of Calgary in Calgary, Alberta, CA.
Description of Sites/Facilities	University of Michigan in Ann Arbor, MI, USA is a tertiary academic medical center. Rockyview General Hospital, associated with the
Enrolling Participants:	University of Calgary, Calgary, Alberta, Canada, is tertiary academic medical referral center for patients with severe asthma.
Study Duration:	1.5 years

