4 STUDY DESIGN

4.1 OVERALL DESIGN

Over an 18-month period we plan to conduct our study in 3 parts as identified in the study timeline table above.

University of Michigan Cohort Discovery, Database Construction, and Baseline Analysis

We plan to utilize existing data analytic tools at the University of Michigan to search the EMR for eligible patients to include in a retrospective cohort as identified by the inclusion criteria in section 5. We estimate that approximately 300 subjects will meet our initial criteria based on a preliminary search. We will then abstract all available clinical information from the EMR, de-identify it (with coded key stored in a separate, secured location), and enter the resulting coded data into a database. Up to 2 years prior to biologic initiation or CT scan (whichever is earlier) and all post-biologic therapy information will be included. Clinical information we will abstract will include demographic information, heights, weights, comorbid illnesses (coded as malignancy, coronary artery disease, diabetes, stroke/TIA, cirrhosis, and CKD), non-biologic asthma medication dosage and frequency of use (OCS, ICS, SABA, LAMA, LABA, montelukast, zileuton, and theophylline), asthma biologic agent (benralizumab, reslizumab, mepolizumab, omalizumab, and dupilumab) start and (if applicable) end dates as well as reason for end date (coded as ineffective, cost, intolerance/allergy, non-compliance, lost to follow-up, and other), FeNO, ACT scores, serum and sputum eosinophil counts, IgE, pulmonary function test parameters (% predicted), hospital/emergency room/urgent care/unscheduled office visits and phone call encounters for asthma or breathing-related complaints, and subjective clinician assessment of asthma control (independently graded by 2 different clinicians interpretation of EMR data). Each subject will also be assigned a phenotype by the Severe Asthma Research Program criteria¹⁵. If a majority of subjects are missing post-bronchodilator data and unable to be clustered by these criteria, we will instead assign adopted clusters from this paper as follows: Cluster 3-Normal FEV1 ($\geq 68\%$ of predicted), eosinophils (< 200 cells/ μL), FeNO (< 25 ppb), and IgE (< 200 UI/ml) and no evidence of atopy; Cluster 4-Reduced FEV1 ($\leq 68\%$ of predicted) with abnormal elevation of eosinophils, FeNO, or IgE and/or evidence of atopy; Cluster 5--Reduced FEV1 ($\leq 68\%$ of predicted) with normal eosinophils, FeNO, or IgE and no evidence of atopy. We do not expect to have any Cluster 1 or 2 patients in our study but will assign them accordingly if present. We will perform similar abstraction procedures for approximately 200 patients in the University of Calgary cohort, and label the data with a tag for this cohort for analytical purposes.

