
For the purposes of our analysis, we will define baseline measurements as the average of all data obtained in the year prior to biologic initiation or, if only one clinical encounter (defined as an office or emergency room visit) is available in this time period, then the average of the 2 clinical encounters immediately prior to biologic initiation will be used with the time frame noted in the database. In order to assess our primary and secondary outcomes we will use the average of all data from 4 to 18 months after biologic initiation or, if only one clinical encounter is available in this time period, the average of the 2 clinical encounters closest to, but not before 4 months after, biologic initiation. If a second biologic is introduced or the initial biologic choice is

changed, we will use all clinical data prior to the change, even if it is before 4 months of use, then follow the above steps to collect new outcome data on the new drug (see **Figure 4**).

[figure not shown]

Figure 4. Baseline and Response Clinical Data Plan.

Since our interest is primarily in finding the ~15% of patients who do not respond to biologics, we have chosen to include partial and complete responders together in our endpoints in order to isolate the non-responder population. Table 1 below will represent the dichotomization of responders and non-responders for each endpoint using the baseline and post-biologic data as detailed above. An exacerbation will be defined as any hospitalization, urgent care, emergency room, or unscheduled office visit for asthma or a breathing-related complaint or a temporary increase of OCS or ICS dosing for 3 or more days with the intent of the increase to treat acute symptoms. For clinician response, clinical encounter notes will be read and interpreted by 2 independent physicians and graded as detailed in the table. Upon completion of all data abstraction the patient will be de-identified as described in data handling below.

	Responder	Non-responder
Exacerbations	Any decrease from baseline	No change from baseline
Hospitalizations	Any decrease from baseline	No change from baseline
Maintenance oral corticosteroid (OCS) use	Any decrease from baseline	No change from baseline

Change in FEV1	$\geq 5\%$ improvement from baseline	<5% improvement from baseline
ACT score	≥ 1 -point improvement from baseline	No change from baseline
Clinician impression of response to therapy	Any improvement in symptoms from baseline	No change from baseline

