5 STUDY POPULATION

5.1 INCLUSION CRITERIA

Our population will include all adults 18 years or older with a diagnosis of asthma (defined as a positive methacholine test, supportive PFTs, or clinician diagnosis with appropriate supporting clinical context) who have been prescribed and taken an FDA-approved biologic medication for severe asthma (mepolizumab, benralizumab, reslizumab, omalizumab, or dupilumab) and have chest CT images in the University of Michigan radiology databases. All patients from the Calgary cohort will be screened in a similar fashion.

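### With every subject treated and response measured from the single year before the biologic, a CT marker of underlying exacerbation rate can pass for a predictor of therapeutic response

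*Combined protocol and SAP*

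**What the plan says.** The Study Description in section 1.1 states that the image analysis will "derive imaging biomarkers that will be able to predict therapeutic response to biologics". The primary objective is more cautious: it seeks markers "associated with the probability of any reduction in pre-treatment baseline exacerbation frequency in a severe asthma population on biologics".

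Section 5.1 admits adults "who have been prescribed and taken an FDA-approved biologic medication for severe asthma", and Calgary patients are screened in a similar way, so neither cohort has untreated patients.

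Section 4.1 fixes the periods:
- Abstraction: "Up to 2 years prior to biologic initiation or CT scan (whichever is earlier) and all post-biologic therapy information will be included".
- Default baseline: "we will define baseline measurements as the average of all data obtained in the year prior to biologic initiation". If that year holds only one encounter, "then the average of the 2 clinical encounters immediately prior to biologic initiation will be used with the time frame noted in the database".
- Outcome: "we will use the average of all data from 4 to 18 months after biologic initiation".
- Exacerbation responder (Table 1): "Any decrease from baseline", with no minimum size.

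Sections 6.1 to 6.3 plan descriptive comparisons, phenotyping and penalised or tree-based prediction models. They contain no untreated contrast, no comparison between pre-treatment periods and no handling of regression to the mean.

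**The concern.** A before-after change in treated patients combines drug effect, natural course and chance. Patients often start an add-on treatment because they have recently been worse than usual, so the last pre-treatment year can overstate their long-run rate. The later fall then includes a return to that rate. Section 4.2 hints at a second route to the same selection, since it notes that CT is seldom done in stable asthma.

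For this study the harm lies in the marker association. A patient with a high underlying rate has less room to fall back after a bad year than a patient with a low rate who happened to have one. A muscle or fat measure that tracks underlying rate would therefore separate apparent responders from apparent non-responders even if the drug acted identically in everyone, or not at all. Validation in Calgary uses the same design, so a replicated association would not settle the matter. Section 3 says the markers are meant to inform clinicians who are deciding whether to start a biologic, and for that use the distinction between prognosis and drug response matters.

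**Working it through.** **Inputs.** From section 4.1: a 12-month baseline, an outcome window of months 4 to 18 (18 − 4 = 14 months), response = any decrease, and about 300 Michigan subjects. The documents state no exacerbation rate, start threshold, effect size or power calculation, so there is no plan figure to reproduce. Assumed: each patient has a stable personal rate, gamma-distributed with mean m and shape k. Counts in year −2, year −1 and follow-up are Poisson given that rate, and follow-up is annualised (count × 12/14). The biologic starts after at least s exacerbations in year −1.

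**Check by formula.** Given a year −1 count y, the expected personal rate is (k + y)/(k/m + 1). With m = 2 and k = 2 this is (2 + y)/2. Under s = 2 the simulated mean year −1 count is 3.50, so the expected rate with an inert drug is (2 + 3.50)/2 = 2.75. That is an apparent reduction of 1 − 2.75/3.50 = 21%. The simulation gives 2.75 for follow-up and also 2.75 for year −2, so the apparent reduction from year −2 is zero.

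**Share with any decrease, inert drug** (shape 1.5 or 3):

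| Assumed mean per year | Start after | Against year −1 | Against year −2 |
|---|---|---|---|
| 1.5–2 | 2 or more | 67–76% | about 50% |
| 1.5–2 | 1 or more | 62–68% | 48–50% |
| 1.5–2 | no selection | 44–49% | same, by symmetry |
| 4–6 | 2 or more | 53–58% | about 49% |

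A wider grid (mean 1, 2 or 3; shape 1 or 2; start after at least 1 or at least 2) gives 58–82% against year −1 and 45–50% against year −2. Apparent mean reductions from year −1 are 6–42%.

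**Marker association.** Take a marker correlated 0.5 with the log personal rate and unrelated to drug effect. On the wider grid with an inert drug, its AUC for response is 0.42–0.45 against year −1, equivalent to 0.55–0.58 with the direction reversed. Against year −2 it is 0.50–0.54. With 300 patients, mean 1.5–2 and a start after 2 or more, such a marker is significant at 5% in 69–78% of simulated studies against year −1 and in 5–6% against year −2. The first figure sets the correlation among patients who start treatment. If it is set before that selection, the figure falls to about one half.

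**An effective drug.** If the drug halves everyone's rate, nobody truly fails to respond. Yet on the wider grid with selection, 4–14% are labelled non-responders against year −1, close to the roughly 15% that section 4.1 hopes to isolate. The same prognostic marker then has an AUC of 0.42–0.47 against year −1 and 0.55–0.58 against year −2. Moving the baseline removes the mean regression, but it does not turn any decrease into a measure of drug effect. A contrast of rates is also needed.

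**The case against.** The strongest reply is that the formal objectives speak only of association, and section 4.2 says the parameters may be able to predict response. That is right, and it limits the charge. The unhedged claim is in the Study Description, although prediction of response also recurs in the rationale and in the endpoint justifications of section 3.

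The size is also open to challenge. Section 5.1 sets no exacerbation threshold, and section 3 names OCS reduction and poor symptom control as common reasons to start. The exacerbation definition in section 4.1 is broad, so rates above 2 a year are plausible. With no selection the mean change under an inert drug is zero. These points stand, which is why the result is a range.

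The share of apparent responders is not itself a false marker association, and the AUC shift is modest. That too stands, but a modest shift is often detectable with 300 patients.

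Year −2 is not a clean control. It is abstracted only where available, section 3 expects missing endpoint data, it may fall on an earlier biologic in patients who switch, and worsening disease would bias it. This limits the remedy but does not rescue the present plan.

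A reader might infer that the plan has no untreated data, or that the second pre-treatment year is ignored. Neither is supported. The baseline year precedes the biologic, and the sparse-encounter fallback can reach into the earlier year. What is missing is any use of that year as a comparison.

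**Conclusion.** The point holds as a limit on interpretation. As planned, an association between a CT marker and response cannot be attributed to drug response rather than to underlying exacerbation rate, and external validation in treated patients would not separate the two.

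The share of no-effect patients counted as responders runs from 44–49% (no selection, 1.5–2 a year) to 67–76% (start after 2 or more, same rates) on the main assumptions, with 53–58% at 4–6 a year. All of these assume stable personal rates and gamma-Poisson counts, and none of the rates or thresholds comes from the documents.

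Two stronger conclusions might be drawn, and the documents support neither. One is that the markers found will be artefacts. That depends on how treatment was started and on how closely a marker tracks underlying rate, and the documents report neither. The other is that the year −2 analysis would establish prediction of drug response. Without untreated patients it can only narrow the alternatives.

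**What to change.** 1. In section 6.3, add a sensitivity analysis that repeats the primary exacerbation analysis with months −24 to −12 as baseline, in patients whose records cover that year and who were free of a biologic during it. Report how many qualify.
2. In the same section, fit a rate model over months −24 to −12, −12 to 0 and 4 to 18, with observation time as offset and a marker-by-period term. Report the contrasts with confidence intervals: follow-up against the earlier year for on-treatment change, and the last year against the earlier year for untreated change.
3. Do not replace these estimates with a rule that accepts markers significant on treatment and non-significant before it. With 300 patients and an inert drug, a purely prognostic marker passed such a rule in 23–24% of simulated studies in one set-up and 42–44% in another.
4. In the section 1.1 Study Description, word the aim as association with, or prognosis for, outcome on a biologic, unless these analyses support more.

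The cost is extra analysis of data already due to be abstracted, plus a wording change; no new patients or scans are needed. The price is a smaller subset, since some patients lack a full or well-recorded second year. Worsening disease or an unrecorded earlier biologic can still bias the comparison, so the ambiguity is reduced but not removed.

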3 OBJECTIVES AND ENDPOINTS

OBJECTIVES	ENDPOINTS	JUSTIFICATION FOR ENDPOINTS
Primary		
To identify imaging biomarkers that are associated with the probability of any reduction in pre-treatment baseline exacerbation frequency in a severe asthma population on biologics	Any reduction in exacerbations when compared to baseline exacerbations	Reduction in exacerbations is the primary clinical endpoint used in phase III trials to get many of the biologics used in asthma approved. Finding imaging biomarkers that associate with and possibly predict which patients will not have a reduction in exacerbations would be critical information for clinicians considering biologic initiation.
Secondary		
To identify imaging biomarkers that are associated with the probability of any post-treatment improvement of FEV1 of 5% or more	5% or greater improvement in FEV1 when compared to baseline FEV1	FEV1 is an important measure of lung function for patients with asthma, and any imaging biomarkers that predict a failure to improve this measure would be clinically useful.
To identify imaging biomarkers that are associated with the probability of any post-treatment reduction in maintenance OCS use	Any reduction in maintenance OCS use when compared to baseline OCS use	OCS are associated with multiple comorbidities, especially in the asthma population. Multiple phase III studies are currently underway to study maintenance OCS reduction in asthma due to this clinical concern and is a common reason for initiating biologics. Any imaging biomarkers that predict a failure to wean OCS after biologic initiation would be clinically useful.
Exploratory		
To identify imaging biomarkers that are associated with the probability of any reduction in pre-treatment baseline hospitalizations for asthma	Any reduction in hospitalizations when compared to baseline hospitalizations	Hospitalizations represent the most severe form of exacerbation and being able to find imaging biomarkers that associate with no improvement in hospitalizations would be clinically significant.
To identify imaging biomarkers that are associated with the probability of any post-treatment improvement in ACT score	Any improvement in ACT score when compared to baseline ACT score	Failure to improve symptoms after biologic initiation is a clinically frustrating scenario and finding imaging biomarkers that can predict this would be important for biologic initiation.

OBJECTIVES	ENDPOINTS	JUSTIFICATION FOR ENDPOINTS

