5.2 EXCLUSION CRITERIA

We will exclude patients with a > 10 pack year history of smoking and those with evidence of emphysema on CT imaging due to concerns that concurrent COPD may be attenuating the effects of the biologic. Those with some scattered bronchiectasis thought to be secondary to severe asthma will not be excluded; however, severe bronchiectasis secondary to other causes will be excluded for the same reason. Furthermore, patients who do not have accessible adequate follow-up information (4 or more months from drug initiation with clear documentation of response) will be excluded from the final analysis in part 3 due to an inability to assess response but will be included in the initial analysis to help with cluster identification.

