6.3 IDENTIFICATION OF BIOMARKERS FOR OUTCOMES

To incorporate high-dimensional morphomic parameters to better stratify patients in regard to their probability of complete response, we will leverage the regularization technique in machine learning to select important variables and develop risk predictive models. To be more specific, elastic net regularization will be utilized to address the high dimensional nature of data derived with analytic morphomics. Elastic net consists of a linear combination of L1 (lasso) and L2 (ridge) penalty to address over-fitting and co-linearity, respectively. In addition, to capture potential non-linear effects among variables, we will also apply random forest and gradient boosting, two highly utilized ensemble tree-based methods. Sample splitting will be used to assess model performance. We will evaluate the accuracy of developed predictive models by various performance measures, including Harrell's Concordance index, integrated cumulative area under the curve, and integrated brier score. The final developed predictive model will be evaluated on an independent dataset from the University of Calgary.

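### The synopsis primary endpoint (a chest-wall-muscle cutoff, or a continuous alternative) has no matching analysis in Section 6.3, and the planned validation is not stated to cover the cutoff

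*Combined protocol and SAP*

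**What the plan says.** The Synopsis (1.1) gives the primary endpoint as "Determine the cutoff value in chest wall muscle size/quality that optimally classifies patients that had and did not have any reduction" in exacerbation frequency from baseline. It then adds a second form: "Alternative (continuous): determine the strength of the linear/non-linear relationship" between the muscle measure and the change in exacerbation frequency. It does not say when the second form would replace the first.

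Section 3 gives the primary endpoint only as the patient-level outcome, "Any reduction in exacerbations when compared to baseline exacerbations". Section 4.1 refers the reader to the statistical section for the detailed analysis.

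Section 6.3 states that "elastic net regularization will be utilized to address the high dimensional nature of data derived with analytic morphomics", and adds random forest and gradient boosting. The quantity to be predicted is the probability of complete response. Performance is to be judged by measures that include Harrell's concordance index, an integrated AUC and the integrated Brier score. Sample splitting is planned for model performance, and the final model goes to the Calgary data.

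**The concern.** An analyst who follows Section 6 to the letter never produces the primary result in the Synopsis. The muscle measure, the meaning of optimal, and the choice between the binary and continuous forms would all be settled after the data are seen.

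A cutoff chosen to separate two groups looks better in the data that chose it than it will elsewhere. Unless the plan says how the cutoff is derived, corrected and tested, a chance split could be reported as a finding, or a real but modest marker could be presented as a better classifier than it is.

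**Working it through.** **1. The sections side by side**

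| Item | Synopsis | Section 6.3 |
|---|---|---|
| Predictor | Chest wall muscle size/quality | All morphomic measures; chest wall muscle not named |
| Outcome | Any reduction in exacerbations | Complete response |
| Result | Optimal cutoff, or continuous relationship | Multivariable prediction models |
| Evaluation | Optimal classification, criterion not given | Concordance index, integrated AUC, integrated Brier score |
| Validation | Calgary, for the biomarkers in general | Sample splitting and Calgary, for the model |

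The outcomes differ in substance: Section 4.1 pools partial with complete responders, whereas 6.3 speaks of complete response. Elastic net may drop the muscle measure altogether. The only named method that yields split points is CART in Section 6.2, and its target is SARP class.

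**2. Inputs for the size of the problem**

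The plan gives no alpha, power or effect size for this endpoint, so there is no figure to reproduce.

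- Michigan: "We estimate that approximately 300 subjects will meet our initial criteria based on a preliminary search".
- Non-responders: "Since our interest is primarily in finding the ~15% of patients who do not respond to biologics", so 0.15 × 300 = 45 against 255. Section 2.1 gives 10-15% complete non-response; the lower end is 0.10 × 300 = 30 against 270.
- Calgary: "approximately 200 patients in the University of Calgary cohort"; at 15%, 0.15 × 200 = 30 against 170.
- Patients without adequate follow-up "will be excluded from the final analysis in part 3 due to an inability to assess response". No rate is given, so 300 is an upper figure.
- Assumed: normal marker, two-sided alpha 0.05, the AUC values, and the 15% (or 10%) share applied to exacerbation response and to Calgary.

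**3. A useless marker, judged on the data that chose the cutoff**

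Youden index J = sensitivity + specificity − 1, maximised over cutoffs in either direction. With no true relation, E[max J] ≈ 0.8687 × √(1/n₁ + 1/n₀).

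- 45/255: √(0.02222 + 0.00392) = 0.1617; × 0.8687 = 0.140. Simulated: 0.136.
- 30/270: √(0.03333 + 0.00370) = 0.1925; × 0.8687 = 0.167. Simulated: 0.161.

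The truth is 0 in both. An uncorrected chi-square test at the best cutoff within the central 80% of values is positive in about 41-43% of datasets. Searching all cutoffs at 45/255 gives 68%. Choosing between two useless measures (assumed correlation 0.5, 45/255) raises mean J to 0.16 and false positives to 67% within the central 80%. This matters because the Synopsis leaves size and quality both open.

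**4. A marker with real signal, 45/255**

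The group separation is d = √2 × z(AUC), and the best attainable J is 2Φ(d/2) − 1.

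| AUC | Best attainable J | Apparent J | True J of chosen cutoff | Overstatement |
|---|---|---|---|---|
| 0.60 | 0.142 | 0.213 | 0.122 | 0.091 |
| 0.65 | 0.215 | 0.278 | 0.198 | 0.080 |
| 0.70 | 0.289 | 0.348 | 0.273 | 0.075 |

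With fewer patients the gap widens. At 30/170 it is 0.293 − 0.193 = 0.100 for AUC 0.65, and 0.363 − 0.269 = 0.094 for AUC 0.70.

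**5. Cutoff frozen in Michigan (45/255), tested in Calgary (30/170)**

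- Useless marker: mean J 0.00, 4.6% false positives.
- AUC 0.60: mean J 0.12, power 28%.
- AUC 0.65: mean J 0.20, power 57%.

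With 30 non-responders, the widest 95% half-width for their proportion correctly classified is 1.96 × √(0.25/30) = 0.18. For 170 responders it is 1.96 × √(0.25/170) = 0.075.

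**The case against.** The strongest reply is that the design already protects against optimism. The Synopsis and the schema send the derived biomarkers or variables to Calgary, Section 4.2 describes a learning cohort and a geographically separate validation cohort, and 6.3 adds sample splitting. This stands in part. A reader might infer that the plan will report the cutoff only on its own data; no section says so. What remains is that none of these provisions names the cutoff, or requires it to be fixed before Calgary is opened.

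A reader might also infer that Section 3 sets a rival primary endpoint. It does not. The primary objective is worded alike in both places, and Section 3 states the patient-level outcome against which the Synopsis cutoff would be judged. The alignment is incomplete, but the outcomes do not conflict.

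Nor do the documents support saying that the study's one hypothesis has no valid analysis. They state no formal hypothesis, the primary objective concerns imaging biomarkers generally, and the 6.3 models can include chest wall measures and capture non-linear effects. What is missing is the specific step that yields and evaluates the cutoff or its continuous counterpart.

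Finally, the useless-marker figures are a worst case, and the plan specifies neither a test at the cutoff nor an alpha. Both points are fair. The figures are conditional, and the overstatement for a marker with real signal is moderate.

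**Conclusion.** The point holds as a gap between the stated primary endpoint and the analysis plan, and it should be closed before the outcome data are analysed. It goes beyond missing detail: predictor, outcome, type of result and performance measures all differ between the Synopsis and 6.3, and the two forms of the endpoint are unranked.

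The optimism is a conditional risk that the plan leaves open. If the chosen cutoff were evaluated on the same Michigan data, apparent J would average about 0.14 (45/255) to 0.16 (30/270) for a useless marker, and be about 0.07-0.08 too high at AUC 0.65-0.70 (45/255). The mismatch between sections rests on the text alone. The sizes rest on the assumptions in step 2 of the working, including no loss from 300; losses would enlarge them.

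**What to change.** In Section 6.3, with Section 3 and the Synopsis aligned to it:

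- State one primary form, binary or continuous, with any reduction in exacerbations as the outcome, and label the other as supportive.
- Name one chest wall muscle measure and one optimality criterion.
- Analyse the continuous relationship and derive the cutoff in Michigan only. Give an optimism-corrected estimate, by bootstrap or by applying the sample splitting already planned to the cutoff itself.
- Freeze the cutoff, then report its sensitivity and specificity with confidence intervals once in Calgary.

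The cost is protocol wording and a little more analysis, with no new patients or procedures. Reported accuracy will be less favourable. Precision in Calgary will be limited, with about 30 non-responders if 15% applies, so the Calgary result should be read through its intervals; a non-significant test there would not show that the marker is useless.
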